We propose to investigate if for patients with an insufficient response to a COBRA-Slim regimen, accelerated access to a short course of anti-TNF therapy already early after treatment initiation (from w8 until w32) could improve outcomes compared to a more traditional treat to target sequence. Current practice requires first the evaluation of the effectiveness of adding or switching to another csDMARD after failure of the initial csDMARD, mostly methotrexate, before a biological can be introduced. An important additional research question would be if providing a bDMARD to insufficient responders to the COBRA-Slim remission induction regimen would be cost-effective compared to continuing treatment adaptations according to the standard COBRA-Slim strategy, taking into account direct and indirect costs.

Assessment and management of risk

This trial can be categorized as a low interventional trial according to the definition of the EU regulation n° 536/2014 for the following reasons:

- The medication (etanercept, defined as etanercept and its biosimilars marketed and reimbursed in Belgium) has a Marketing Authorization in Belgium
- According to the protocol the medication is used in accordance with the indication as mentioned in the European Marketing Authorization
- Any additional diagnostic or monitoring procedures do not deviate from routine clinical practice, with the exception of the completion of some questionnaires

2 Objectives and outcome measures/endpoints

Primary objective

To compare in an early RA population with insufficient response (not achieving DAS28CRP \leq 3.2) to COBRA-Slim remission induction, the long-term effectiveness of accelerated access to a 24 weeks course of anti-TNF therapy (etanercept) within a time window from w8 up to w32, versus further treatment adaptation according to the standard COBRA-Slim strategy.

For this purpose, the area under the DAS28CRP curve from BL until w104 will be assessed. This outcome parameter is considered to be clinically very relevant, since it reflects the overall evolution in disease burden over the first 2 years of treatment, taking into account the speed and stability of the response and the need for consecutive treatment adaptations.

Secondary objectives

Main secondary objective

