In this pragmatic, prospective, multicenter, randomized, controlled trial of 2-year duration, 442 patients with early RA (≤ 1 year), previously untreated with DMARDs (disease modifying anti-rheumatic drugs), will be included. A subgroup of insufficient responders to the initial COBRA-Slim remission induction regimen will be randomly assigned, during a time window between w8 and w32, to 2 different treatment strategies.

Randomization will be balanced according to time-point of randomization, BL disease activity and RF/ACPA status using the minimization technique (see statistical plan). Patients who do not meet the criteria for randomization, during the so-called accelerated access period, will still follow the common adaptation strategy during the remaining part of the study.

Initial protocol-based treat to target period (BL until w32):

All participants will receive at BL a COBRA-Slim remission induction regimen, which includes:

- Methotrexate 15 mg PO weekly (starting from 10 mg weekly for 2 weeks)
- Step down scheme of GC: 30-20-12,5-10-7,5-5 mg prednisone PO daily, each for 7 days except for the lowest dose of 5 mg, this will be maintained until w28 and then tapered to 2.5 mg daily for two weeks before stopping completely.

In case at any evaluation moment from w4 until w32 (not included) patients do not reach low disease activity (LDA = DAS28CRP \leq 3.2), the MTX dose will be increased to 20 mg PO weekly.

If after this first adaptation patients still not achieve or maintain a sufficient response during the period from week 8 until 32 (the accelerated access period), they will be considered insufficient responders.

Insufficient responders are defined as:

Patients not reaching LDA (DAS28CRP \leq 3.2) at any evaluation moment from week 8 until 32 after the first adaptation (a previous MTX increase).

Patients not reaching remission (DAS28CRP $<$ 2.6) at the week 32 evaluation visit irrespective of a previous MTX increase.

These insufficient responders will be randomly assigned to one of two different treatment strategies:

Group 1: Standard COBRA-Slim Induction:

Addition of leflunomide 10mg PO daily as the next step in the protocol-based CareRA2020 treatment adaptation scheme.

If target of LDA is still not reached or maintained minimally 12 weeks after the initiation of Leflunomide, treatment has to be adapted according to the next step of the adaptation scheme.

Group 2: COBRA-Slim Bio-induction with accelerated access to anti TNF:

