Randomized at W24	X	X	X	X		X		X		X	X	X		X	X			X
Randomized at W32	X	X	X	X		X		X		X	X	X	X	X	X	X	X	X
Not randomized	X	X	X	X		X		X		X	X	X		X	X	X	X	X

General mandatory visit	
General optional visit	

Mandatory visits for randomized patients	R+28w
	R+24w
	R+16w
	R+8w

In case of restrictions in the usual outpatient care organization at the participating rheumatology centers due to governmental or local regulations (e.g. related to the outbreak of an epidemic), regular outpatient visits can be replaced by a telephone consultation when required to reduce risks for patients and health workers .

During this telephone consultation, one should gather as much clinical data as possible with regards to the visit it is replacing. Patients should also be encouraged to continue completing their PROs. When this is done electronically, patients will be reminded of their questionnaires as usual. In case these PROs are completed on paper, the site should provide patients with a paper version of the PROs and a prepaid envelope to return them to the site.

During a telephone consultation, the rheumatologist cannot score patients' joints. Therefore, it is suggested to provide the patients with a template for self-evaluation of the joints on tenderness and swelling. Literature suggests this could be a reliable alternative. The procedure to distribute this homunculus is the same as described for the PROs: for patients with a known email address by email, for the others by regular mail.

Regular lab testing for CRP, hematology, liver- and kidney function is also a point of attention. During the telephone consultation it should be checked if blood sampling was done recently. If not, the general practitioner can be asked to take a blood sample, depending on the regulations.

If after a telephone consultation, the investigator is convinced that the disease activity is not sufficiently well controlled and there is a need for treatment adaptations, a traditional

consultation at the outpatient clinic might be justifiable. At that time the mandatory visit should be completed and a randomization procedure must be performed if required by the protocol.

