In case of an epidemic like the COVID-19 outbreak, the health of patients and coworkers are the first priority. On the other hand, adequate follow-up of patients, with a chronic condition and in need of a chronic treatment, is essential. Interruption of treatment is contraindicated, not for conventional nor for biological or targeted synthetic DMARDs, except in case of active infection or other complications and preferably on the advice of the treating rheumatologist.

Data collected during telephone consultations will be transcribed by the sites at the correct visit page in the e-CRF, marking the box of the telephone visit next to the date field. This way data management can clearly discriminate between data collected by phone and during outpatient consultations.

BL data (w0)

The following information will be captured from routine clinical data (SoC) at Week 0 visit:

- Clinical/Rheumatologic examination
- Joint Count: TJC, SJC
- Weight
- ESR and CRP (in case screening blood samples were taken within 5 days, these values can be used).
- DAS28CRP/DAS28ESR (in case screening blood samples were taken within 5 days, these values can be used)
- VAS PhGA/GH/pain/fatigue
- HAQ
- Relevant concomitant medication
- Relevant side effects
- Changes in employment status

Apart from the above information following PROs will be collected from the patients specifically for the study:

- RAID
- EQ5D/WPAI

Trial assessments

(A schematic overview can be found at page 21)

At week 4, 12, 20, 28, 48, 56, 68, 82, 95 or unscheduled visit following data are captured as part of routine clinical data collection (SoC):

- Clinical/Rheumatologic examination
- Joint Count: TJC, SJC
- Weight
- ESR and CRP
- DAS28CRP/DAS28ESR
- VAS PhGA/GH/pain/fatigue
- Relevant concomitant medication
- Relevant side effects
- Changes in employment status

Randomization procedure is optional and is preferably done at the dedicated visits (w8, 16, 24 or 32). In case randomization is required in between these visits, when LDA is not reached, it is allowed at week 12, 20 and 28.

At week 8, 16, 24, 32, 40, 64, 78 and 91 following data are captured as part of routine clinical data collection (SoC):

- Clinical/Rheumatologic examination
- Changes in co-morbidities assessment (co-morbidity shortlist only at w32)
- Joint Count: TJC, SJC
- ESR and CRP
- DAS28CRP/DAS28ESR
- VAS PhGA/GH/pain/fatigue
- HAQ
- X-ray (Sharp/van der Heijde Score) only for w24 visit
- Relevant concomitant medication

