To properly estimate the number of patients that will belong to this w8-w32 insufficient responder group (target of LDA: DAS28CRP \leq 3.2), data from the previous CareRA trial were used, in which ‘COBRA-Slim’ was compared with other remission induction schemes (Verschueren et al, 2015). In the CareRA trial population around 25% of patients required a second treatment adaptation because they did not reach LDA during the remission induction phase after a first adaptation of MTX dose increase to 20 mg.

Expected difference in effect

The early insufficient responders in the previous CareRA trial had a mean AUC under the DAS28CRP curve of 351.3 (SD 103) after 2 years. We estimate that patients in this insufficient responder group, when given the opportunity to have accelerated access to a short course of etanercept, will have an increase in effect size, reflected by a decrease in AUC at w104 in comparison to the reference arm. We consider a 20% decrease in AUC (from 351 to 281) to be clinically relevant and assume the same standard deviation. A 20% reduction in AUC over the first 104 weeks of treatment would reflect an important decrease of the overall disease burden. Additionally, we believe that this is the minimum effect size to consider an early access to anti-TNF to be cost-effective.

Sample size calculation of insufficient responders

For a superiority design, with a two-sided alpha of 0.05, the null and alternative hypotheses are:

- **Null hypothesis:** In early insufficient responders to COBRA-Slim induction therapy, accelerated access to anti-TNF therapy leads to the same AUC compared to treatment

adaptation according to the standard COBRA-Slim strategy after 104 weeks (there is no difference in AUC in early insufficient responders). $H0: \delta = 0$

- **Alternative hypothesis:** In early insufficient responders to COBRA-Slim induction therapy, accelerated access to anti-TNF therapy can be considered as superior to the standard COBRA-Slim strategy. $H1: \delta \neq 0$

These are the parameters taken into account for the sample size calculation, using PASS 14 software (PASS 14 Power Analysis and Sample Size Software, 2015. NCSS, LLC. Kaysville, Utah, USA, ncss.com/software/pass):

- Calculation of Superiority / Test for Two means (likelihood ratio test).
- Allocation of 1:1
- Power of 0.80
- α was set at 0.05.

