Area under the curve of DAS28CRP over 104 weeks (long term effectiveness) in insufficient responders (w8-w32) randomized to either COBRA-Slim Bio-Induction or Standard COBRA-Slim Induction.

Method of analysis

Because missing data are expected, we will use the method from Bell et al to compare AUC between treatment arms based on a mixed model for repeated measures (MMRM) with DAS28CRP as the outcome (Bell et al, 2014). The model will be adjusted for the variables used in the minimization algorithm for treatment assignment (moment of randomization; between w8 and w32 but preferably at the dedicated time points w8, w16, w24, or w32 from baseline), DAS28CRP at baseline, and RF/ACPA status (see table). The effect of treatment arm is corrected for minimization factors to obtain correct P values and confidence intervals and to avoid an unnecessary loss in power (Kahan & Morris, BMJ 2012). The model will include the following mandatory visits: w4, w8, w16, w24, w32, w40, w52, w64, w78, w91, and w104.

Table: Minimization variables.

Variable	Description
Timing of randomization	Randomization is possible between w8 and w32 preferably at the dedicated time points (w8, w16, w24, w32)
Disease activity at baseline	DAS28CRP score categorized as low (≤ 3.2), moderate (> 3.2 to ≤ 5.1), or high (> 5.1).
RF and/or ACPA status	Positive serology of either RF or ACPA versus negative serology for both

We will report the estimated difference in AUC between study arms together with a 95% confidence interval. The confidence interval mainly helps to interpret the uncertainty around the treatment effect, but it can also reveal whether the treatment effect is statistically significant at the 5% level.

Plans for handling multiple comparisons, missing data, non-compliers, spurious data and withdrawals in analysis

Missing values for the primary endpoint may arise because not all measurements to derive the presence of remission are available, or because patients withdraw from the study. We expect around 21% dropouts based on the CareRA trial. Most will be lost to follow-up or due to patient withdrawal; occasionally patients drop out because of death or logistic reasons (Verschueren et al, 2016).

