We will compare dropout between arms. More specifically, the amount of dropout, the time point of dropout, and the reason for dropout will be compared (Committee for Medicinal Products for Human Use, 2010). If this is equal, there is less concern about systematic bias (Vickers & Altman, 2013). We will also compare baseline measurements and measurements at the randomization visit between patients who do and do not drop out up until week 104.

The MMRM method assumes that data are ‘missing at random’ (MAR). This means that missing values are completely random conditional on other observed measurements. We believe that MAR is a plausible assumption. Last observation carried forward, although often used, is an implausible assumption and will not be considered in this trial (Mallinckrodt et al, 2001; Jansen et al, 2006; White et al, 2012; Jiang et al, 2015).

We plan two sensitivity analyses (EMA guideline):

1. An alternative analysis option under the MAR assumption of missing values involves multiple imputation of missing DAS28CRP values. After imputation, the primary endpoint (AUC of DAS28-CRP over 104 weeks) will be analyzed using linear regression. Predictor variables in the model will be treatment arm and the minimization factors, which are the timing of randomization, disease activity at baseline, and RF and/or ACPA status.

Multiple imputation using fully conditional specification will be used to handle missing data (Sterne et al, 2009; Spratt et al 2010; van Buuren 2015; Lee et al, 2016). The multiple imputation procedure will by default include the variables in the analysis model: DAS28CRP at the timepoints used to calculate the AUC, treatment arm, time of

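### Post-baseline DAS28CRP up to randomisation is a covariate in neither the primary MMRM nor sensitivity analysis 1: the plan is valid, but may forgo some precision

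*Combined protocol and SAP*

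**What the plan says.** - **Window.** Section 2, Primary objective: "the area under the DAS28CRP curve from BL until w104 will be assessed".
- **Common treatment first.** Section 3, Initial protocol-based treat to target period: "All participants will receive at BL a COBRA-Slim remission induction regimen, which includes" the components then listed. The strategies diverge only when an insufficient responder is randomised, from w8 up to and including w32.
- **Primary model.** Section 10, Method of analysis: an MMRM adjusted for timing of randomisation, DAS28CRP at baseline and RF/ACPA status. "The model will include the following mandatory visits: w4, w8, w16, w24, w32, w40, w52, w64, w78, w91, and w104". The arm-by-visit terms and the weights that turn visit means into an AUC are not written out; the AUC method is deferred to a cited source.
- **Sensitivity analysis 1.** After multiple imputation the AUC is analysed by linear regression: "Predictor variables in the model will be treatment arm and the minimization factors". Baseline disease activity as a minimisation factor has three categories. The imputation model contains DAS28CRP at all time points used for the AUC.
- **Other use of randomisation-visit values.** Section 10 compares them between patients who do and do not drop out.
- **Off-schedule randomisation.** Section 6, Trial assessments: "In case randomization is required in between these visits, when LDA is not reached, it is allowed at week 12, 20 and 28". None of these three weeks is a listed model visit.

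**The concern.** Before a patient is randomised the arms cannot differ in expectation. Scores from that period add patient-to-patient variation to the AUC but no treatment effect, and they may predict the rest of the patient's curve. A regression that conditions on them removes the predictable part of the variance.

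Having those scores as outcomes in an MMRM is not the same thing. If each visit has its own free arm term, a chance arm difference at w4 or w8 is estimated as though it were an effect and goes into the AUC contrast. If the arm terms are fixed at zero before randomisation, the same scores act as covariates. The plan does not say which applies.

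At stake is the width of the confidence interval in a comparison of about 104 randomised patients.

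**Working it through.** **1. The plan's own figures.** Inputs from Section 10, Sample size calculation: means 351 and 281 (difference 70), SD 103, two-sided alpha 0.05, 1:1 allocation. Two-sample t-test, noncentrality = 70 / (103 × √(2/n)), n per arm:
- 70 completers: 70 / (103 × √(2/35)) = 2.84, 68 df, power 80.0%.
- 82 completers: 70 / (103 × √(2/41)) = 3.08, 80 df, power 86.0%.

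Both agree with the plan. The calculation uses the unadjusted SD, so no stated figure depends on further covariates.

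**2. Share of the window before randomisation** (week / 104):

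| w8 | w12 | w16 | w20 | w24 | w28 | w32 |
|---|---|---|---|---|---|---|
| 7.7% | 11.5% | 15.4% | 19.2% | 23.1% | 26.9% | 30.8% |

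**3. Does having early visits as outcomes adjust for them?** Illustration with assumed covariance: 82 patients with complete data, all randomised at w8, visits w4 to w104, no covariates.
- Free arm-by-visit terms: AUC difference 12.34, SE 16.03, identical to the raw difference in mean AUC. The w4 and w8 scores adjusted nothing.
- Arm terms zero at w4 and w8: SE 11.26, a variance ratio of (11.26/16.03)² = 0.49.

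This shows the mechanism, not the size for this trial. The plan also adjusts for baseline DAS28CRP, which would take up part of that gain.

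**4. Possible size in sensitivity analysis 1.** The figures are variance ratios, with added covariates over planned covariates, on complete data. All correlation structures are assumed.
- Randomisation-visit score alone, two sets of structures not calibrated to 25% randomised or SD 103: 0.50 to 0.98 and 0.57 to 0.98.
- Randomisation-visit score plus mean score from baseline to randomisation, eight structures calibrated to 25% randomised, control mean 351, SD 103, effect −70 and n = 104: 0.35, 0.53, 0.42 (persistent patient differences); 0.83, 0.86 (mixed); 0.99, 0.99, 0.97 (differences arising after randomisation).

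The persistent structures need a patient-level SD of 1.6 to 1.8 DAS28CRP points, whereas an AUC SD of 103 over 104 weeks is 103/104 = 0.99 points of average level. More than about 40% reduction should therefore not be relied on.

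Part of the gain may come from replacing the three-category baseline by something finer. In the uncalibrated structure with the strongest patient effect, continuous baseline DAS28CRP alone explained an extra 0.41 of the AUC variance, against 0.50 for the randomisation-visit score.

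**5. What a given gain would be worth.** With R² the extra share of AUC variance explained (assumed), SD becomes 103 × √(1 − R²), and one more df is spent:

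| R² | SE ratio | Power, 70 completers | Power, 82 completers |
|---|---|---|---|
| 0 | 1.000 | 80.0% | 86.0% |
| 0.10 | 0.949 | 84.0% | 89.3% |
| 0.20 | 0.894 | 88.0% | 92.5% |
| 0.40 | 0.775 | 95.1% | 97.5% |

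At R² = 0 the lost df costs about 0.01 to 0.02 percentage points of power.

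**The case against.** - **This is preference, not defect.** The sponsor chose its adjustment set and gave reasons. That stands, so the point is an improvement and not a correction. The sponsor's stated reasons do include not losing power needlessly, which is the same argument.
- **Pre-randomisation data are already used.** Baseline DAS28CRP is itself pre-randomisation and both models adjust for it. Scores at the listed visits from w4 to w32 are MMRM outcomes and inputs to the imputation model. This stands: the point covers only post-baseline scores, and only their role as covariates.
- **The primary-model part is conditional.** It depends on arm-by-visit terms that Section 10 does not state. This stands in full; only the sensitivity-analysis-1 part is unconditional.
- **The size is unknown.** This stands. The range reflects chosen structures and no value within it is favoured.
- **Extra by-visit covariates would burden the MMRM.** Two covariates at 11 visits add up to 22 mean parameters. For a patient randomised at w8, the w8 outcome would equal its own covariate. This stands, and such covariates are not recommended there.
- **Simulated coverage.** In an MMRM with the planned covariates and about 20% dropout missing at random, 95% intervals covered 91.8% to 95.8% over the eight calibrated structures (Monte Carlo SE about 1 point). The lowest value is below nominal and unexplained. Absence of bias rests on randomisation, not on these runs.

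**Conclusion.** The point holds as a modest matter of precision. DAS28CRP after baseline, up to and including the randomisation visit, is a covariate in neither analysis model, although 7.7% to 30.8% of the AUC window precedes randomisation. In sensitivity analysis 1 some precision is forgone. In the primary MMRM this is so only if the arm-by-visit terms are unconstrained. The variance reduction available is between close to nil and about 40%, under correlations that the documents do not give.

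A reader might infer three stronger things, none of which the documents support:
- **Bias or false positives from the pre-randomisation stretch.** Arms are equal in expectation there, so the planned contrast remains valid.
- **An underpowered trial.** The planning group "had a mean AUC under the DAS28CRP curve of 351.3 (SD 103) after 2 years", so the planning SD already refers to a two-year AUC, and 80% and 86% reproduce without further adjustment.
- **Early data that go unused.** Apart from randomisation-visit scores at w12, w20 and w28, which lie outside the listed visits, they enter as outcomes and in the imputation.

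**What to change.** Keep the baseline-to-w104 endpoint and make these changes:

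1. **Sensitivity analysis 1.** Add DAS28CRP at the randomisation visit as one covariate; optionally add the mean score from baseline to randomisation. This also brings in the qualifying score of patients randomised at w12, w20 or w28.
2. **Missing values.** Section 6 notes "During a telephone consultation, the rheumatologist cannot score" joints, so a score can be missing. Where control seems insufficient it foresees a clinic visit: "At that time the mandatory visit should be completed and a randomization procedure must be performed if required by the protocol". Missing randomisation-visit scores should therefore be uncommon. Impute them in the multiple imputation already planned, deriving the covariate from the imputed visit value when randomisation falls on a listed visit.
3. **Primary MMRM.** Write out the arm-by-visit terms and the AUC weights, including how baseline enters, since the listed visits start at w4. Trapezoid weights for w0, 4, 8, 16, 24, 32, 40, 52, 64, 78, 91 and 104 would be 2, 4, 6, 8, 8, 8, 10, 12, 13, 13.5, 13 and 6.5 (sum 104). Set the arm effect to zero at visits at or before each patient's own randomisation, and state the mix of randomisation times over which the contrast is averaged. Do not add by-visit covariates built from scores that are also outcomes.

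If the arm terms are already constrained in this way, the MMRM needs no change beyond stating so; randomisation-visit scores at w12, w20 and w28 would still lie outside it.

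**Cost.** One or two parameters in the regression, no new data, and a gain that may be small. Section 10, Other statistical considerations, requires a protocol amendment for any deviation from the plan. The trial is open-label and the steering committee may see outcome data if needed, so the amendment should be fixed before outcome data are analysed.
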